11.6.5. Biomarker

11.6.5.1. Biomarkers and Source

SAM	Serum	Nasal Wash	BAL
IL-6, IL-10, IP- 10, IL-8, MPO, NE, IL-1b	Procalcitonin	IL-6, IL-10, IP-10 , IL-8 , MPO , NE , IL-1b	IL-6, IL-10, IP- 10 , IL-8 , MPO , NE , IL- 1b
	C1M, C3M, EL-NE	Neutrophil Cell Counts	
SP-D, sRAGE,	SP-D, sRAGE	SP-D, sRAGE	SP-D, sRAGE

Biomarker

- If a laboratory value which is expected to have a numeric value for summary purposes, has a non-detectable level reported in the database, where the numeric value is missing, but typically a character value starting with '<x' or '>x' (or indicated as less than x or greater than x in the comment field) is present, the number of significant digits in the observed values will be used to determine how much to add or subtract in order to impute the corresponding numeric value.
 - Example 1: 2 Significant Digits = '< x ' becomes x 0.01
 - Example 2: 1 Significant Digit = '> x' becomes x + 0.1
 - Example 3: 0 Significant Digits = '< x' becomes x 1

AUC of Biomarker

- The area under the curve (AUC) to Day 5, Day 45, and PT Day 3 of biomarker as measured by the level of biomarker from biomarkers source:
- The AUC will be calculated as

AUC (0-Day x) =
$$\sum_{0-1} \{ \frac{1}{2} (C_i + C_{i+1}) (t_{i+1} - t_i) \}$$

Where,

C_i = level of biomarker at actual time point i in Day

t_i = actual time of assessment for time point i in Day

i = actual time of assessment in Day (e.g. Day 1, 3, 5, 8, 16, 24, 32, day 45)

I = last i (Day 5, Day 45, or PT Day 3)

- Actual study day will be used for the AUC calculation.
- When baseline value of a biomarker is missing, AUC for the biomarker will be missing.
- When a subject has only baseline value, AUC will be missing.
- When value of a biomarker is missing between visits, there will be no imputation for the missing value, e.g. subject has day 1, 3, 5, 8, 16, 32, 45 values, and day 24 value is missing, day 24's value will not be imputed, AUC will be calculated using day 1,3,5, 8,16, 32, and 45 values.
- When value of a biomarker is missing at the end, last observation carried forward (LOCF) will be used to impute missing value, e.g, subject has day 1, 3, 5, 8, 16, 24, 32 values and day 45 is missing, day 45 value will be imputed using day 32 value (day 45 value will be assumed the same as day 32 value).
- The value of the AUC(0-45) biomarker is missing if there is no assessment beyond week 24.
- The length of time from Baseline to PT Day 3 visit will vary for subjects who prematurely
 discontinue the study and so the biomarker will also vary.

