4.2. Treatment Arms and Duration

Subjects will be randomized in a 2:2:1 ratio to receive:

- 15 mg FBE IV DNX BID +75 mg OSV BID;
- 50 mg FBE IV DNX BID + 75 mg OSV BID; or
- IV DNX placebo BID + 75 mg OSV BID

Treatment duration will be up to 5 days ([Figure 2](#)). The investigator may elect to continue open-label oseltamivir treatment. If a subject is discharged from the hospital in less than 5 days, treatment with IV DNX will discontinue, irrespective of whether the investigator elects to continue oral OSV treatment at discharge. Follow up will continue until Day 45 for all subjects.

Figure 2 Study Schematic

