		Baseline/ Study Day 1 ^a	Study Day 2	Study Day 3	Study Day 4	Study Day 5 /day of last dose ^a	Study Day 6 if applicable ^b	
Study Treatments								
Administration of investigational medication (IV) and oseltamivir (oral) twice daily		X	X	X	X	X	X	

- a. A 'Day' is defined as a 24 hour period (Treatment Day), therefore depending on the start time of the first dose of IV DNX, a Treatment Day may span two calendar days.
- b. Day 6 assessments only applicable if last day of dose of randomized treatment is on Day 6 (i.e for subjects who received first dose after 12 noon on Baseline/Day 1.
- c. Physical exam to be performed twice daily for subjects in the sentine cohort.
- d. Enrollment into the study will be based on history of diagnosis of HIV and liver disease. Blood samples will be analyzed after enrollment to retrospectively determine if subject is HIV, Hep B or Hep C positive; however, results will not be available until after completion of dosing.
- e. Influenza symptoms to be assessed only at baseline for inclusion.
- f. Enrollment into the study will be based on any history of diagnosis of HIV and liver disease.
- g. Chest X-ray at Baseline and whenever clinically indicated.
- h. ECG: For the ECG on Baseline/Day 1, one 12-lead ECG (can be done within approximately 24 hours prior to dosing). At Baseline and on Day 5 or last treatment day, a monitoring strip can be utilized if a 12-lead ECG cannot be performed.
- i. Concomitant medications for influenza treatment of the current episode to be recorded from Day -7 (i.e. one week prior to baseline), if available.
- j. Complications of influenza such as bacterial pneumonia, pneumothorax, pleural effusion, ARDS, myositis, encephalitis, myocarditis, and associated antibiotic use will be recorded on all assessment days.
- k. Vital signs and ventilation status to be assessed three times daily during the treatment period between approximately 8 AM and 8 PM.
- l. Katz ADL score collected once daily while hospitalized.
- m. Activity level to be recorded as one of three responses (bed rest, limited ambulation or unrestricted) everyday while hospitalized
- n. Chemistry panel including Liver Function Tests to be required once every other day during treatment (local testing (L) of LFTs for subject management as well as central laboratory testing (C)).

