- o. Serum creatinine level required at Baseline and twice daily during treatment for subjects in the sentinel cohort. For all other subjects, serum creatinine level required at Baseline and once daily during treatment (local testing (L) for subject management as well as central testing(C)).
- p. Hematology panel including CBC with differential required every other day during treatment (local testing (L) for subject management as well as central testing(C))
- q. Urine output to be measured twice daily for subjects in the sentinel cohort.
- r. Ultrasensitive urine or blood pregnancy test required in women of childbearing potential prior to dosing and 3 days post last dose of study treatment.
- s. Nasopharyngeal swab will be used for influenza Subtype RT-PCR, qRT-PCR, quantitative culture and may also be used for rapid influenza diagnosis; Will also be used for viral genotyping and phenotyping if needed and multiplex PCR assay.
- t. Nasal swab collected for influenza diagnostic test or other local test for influenza diagnosis

- u. BAL samples (for biomarkers) are requested only if the procedure/sampling is being carried out for routine management of the patient and at any timepoint throughout the study
- v. Endotracheal aspirates (biomarkers/neutrophil counts) are required for subjects who are intubated.
- w. Nasal samples for biomarkers will be collected at the days indicated from all subjects using nasal SAM strips.
- x. An optional procedure, nasal wash, will be used to collect nasal samples from as many non-intubated subjects as feasible.
- y. PK samples will be drawn on Day 1 (pre-dose), Days 3 and 5 to coincide with PD measurements (nasal washes if done, endotracheal samples and a blood draw for exploratory biomarkers). In sentinel cohort 1 (less severe subjects with normal renal function), PK samples will be additionally drawn on Day 3 at pre-dose, and 0.5, 1 (end of infusion), 1.5, 2, 3, 4, 8 and 12 hours post-dose. **Note: PK draws must be collected from the opposite arm from the infusion arm.**
- z. Informed consent for optional substudies (e.g., genetic research and transcriptomics), must be obtained before collecting samples. In subjects who consent, a blood sample for genetic research is collected at the baseline visit, or at the earliest point possible during the treatment period for genetic research testing; blood samples for transcriptomics are taken on each of the indicated days and used to evaluate changes in transcriptome profiles.

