Table 4 Time and Events Table: Post-Treatment and Post-Discharge Assessments

Procedures	Post-Discharge Visits/TCs and Assessments Outpatient ^a					
	PT Day 3 (Visit)	Study Day 8 (TC)	Study Day 15 (TC)	Study Day 22 (TC)	Study Day 30 (TC)	Study Day 45 (Visit)
Safety/Efficacy Assessments						
Adverse events	X	X	X	X	X	X
Concomitant medications	X	X	X	X	X	X
Brief Physical Exam	X					X
Complications of influenza / associated antibiotic use ^b	X	X	X	X	X	X
Temperature	X	X	X	X	X	X
Other Vital signs (HR, BP, respiratory rate, oxygen saturation, ventilation status) ^c	X					X
Flu PRO ^d	Daily through Day 14	Daily through Day 14	X	X	X	X
Katz Activities of Daily Living ^e	X	X	X	X	X	X
Activity level ^f	Daily through Day 14	Daily through Day 14	X	X	X	X
Laboratory Assessments						
Clinical chemistry including LFTs ^g (Local+Central)	X					X
Serum Creatinine ^h (Local+Central)	X					X
Hematology ⁱ (Local+Central)	X					X
Pregnancy test ^j	X					
Nasopharyngeal swabs	X					
Exploratory Biomarkers (Blood Sample) ^k	X					X
Transcriptomics (blood sample) ^l	X					X
Nasal SAM strips (biomarkers) ^m	X					X
Nasal washes ⁿ	X					X
Hospital Readmission Status	X	X	X	X	X	X

a. Following discharge from hospital, outpatient clinic visit/TC schedule of assessments will be followed for those patients who are discharged before Day 45. For 5 days treatment, PT Day 3 will be the same as Day 8 and will be a clinic visit.

- b. Complications of influenza such as bacterial pneumonia, pneumothorax, pleural effusion, ARDS, myositis, encephalitis, myocarditis, and associated antibiotic use will be recorded on all assessment days.
- c. Vital signs and ventilation status will be assessed at clinic visits (PT Day 3 and Day 45).
- d. FLU PRO to be measured once daily through Study Day 14.
- e. Activities of Daily Living (Katz Scale) to be done at clinic visits and at TCs.
- f. Activity level assessed by reporting on a 3 point scale of bed rest (1), limited ambulation (2) or unrestricted (3) to be done daily through Study Day 14.
- g. Clinical chemistry including LFTs to be required once every other day until PT Day 3 (for LFTs, local testing for subject management until PT Day 3; central testing for all assessments, including at Day 45).
- h. Serum creatinine required once every day until PT Day 3 (local testing for subject management until PT Day 3; central testing for all assessments, including at Day 45).

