- i. Hematology panel including CBC with differential required once every other day until PT Day 3 (local testing for subject management until PT Day 3; central testing for all assessments, including at Day 45).
- j. Ultrasensitive urine pregnancy test required in women of childbearing potential on PT Day 3.
- k. Blood samples will be collected for exploratory biomarkers at PT Day 3, and at Study Day 45.
- l. Blood samples for transcriptomics will be collected on PT Day 3 and Study Day 45 and are optional. Samples will be collected only from those subjects who provide informed consent for genetic research.
- m. Nasal samples for biomarkers will be collected at PT Day 3 and Study Day 45 from all subjects using nasal SAM strips. In addition, an optional procedure, nasal wash, will be used to collect nasal samples from as many non-intubated subjects as feasible.

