7.3.4. Virologic Measures and Biomarker Sampling

Samples for virologic measures and biomarker sampling will be collected locally as in the Time and Events Tables (Section 7.1). These samples will include nasal swabs, nasopharyngeal swabs, nasal samples (SAM strips and optional nasal washes), endotracheal aspirates (from intubated subjects), whole blood samples (ribonucleic acid [RNA] transcriptome analysis, deoxyribonucleic acid [DNA]), serum, and BAL samples from subjects where it is part of routine management. When multiple respiratory samples are to be taken at any visit, samples will be collected in the following order (Table 6).

Table 6 Sampling Order of Respiratory Samples for Virologic and Biomarker Assessments

Sequence of Collection	Sample Type	Study Day (inpatients)	Outpatient Assessments	Number and location of samples	Purpose
1	Nasal swab or nasopharyngeal swab	Day 1	N/A	Nare 1	Influenza diagnostic test
2	Nasal SAM strips	Day 1, 3, 5, 8, 16, 24, 32; also at discharge or Day 45	PT Day 3, Day 45	Both nares	Biomarker analysis
3	Nasopharyngeal swabs	Day 1, 3, 5, 8, 12, 16, 20, 24, 28, 32;	PT Day 3	Nare 2	Virology analysis
4	Nasal wash ^a	Day 1, 3, 5, 8, 16, 24, 32; also at discharge or Day 45	PT Day 3, Day 45	Both nares	Neutrophil counts/biomarker analyses
	Endotracheal samples ^b	Day 1, 3, 5, 8, 16, 24, 32, 45	N/A	ET aspirate	Neutrophil counts/biomarker analyses

a. Requested from subjects who are not intubated (optional procedure).

b. Required from subjects who are intubated.

- Nasal swabs will be collected at baseline to confirm influenza infection with a rapid influenza diagnostic test provided by GSK or other local test.
- Nasopharyngeal swabs will be collected for influenza Subtype RT-PCR, qRT-PCR, quantitative culture and may also be used for rapid influenza diagnosis. Nasopharyngeal samples will also be used for viral genotyping and phenotyping if needed and for multiplex PCR assay.
- Endotracheal (ET) aspirates will be collected from subjects who are intubated. The endotracheal samples will be used for biomarker evaluation and neutrophil counts (Section 7.6).
- Nasal SAM strips will be used to collect nasal samples and will be used for biomarker evaluation.

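### SAP 11.6.5.1 makes AUC(0-45) depend on an assessment beyond week 24 (Day 168) in a 45-day study, so as written it is missing for every subject

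*SAP*

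**What the plan says.** SAP section 11.6.5.1 defines a biomarker area under the curve to Day 5, Day 45 and PT Day 3, using the trapezoid rule on actual study days. The latest time point in its formula is Day 45. The bullets below the formula give the missing-data rules:

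- A missing value between visits is not imputed. The example has Day 24 missing and calculates the AUC from the remaining days up to Day 45.
- A missing last value is carried forward. In the example, "day 45 value will be imputed using day 32 value".
- A further condition applies to the longest window only: "The value of the AUC(0-45) biomarker is missing if there is no assessment beyond week 24".

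SAP section 11.13.12 plots AUC(0-5), AUC(0-45) and AUC(0-PT Day 3) against time to clinical response or time to respiratory response in Figures 6.2 to 6.9, with a regression line per treatment group.

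On study length, protocol section 4.2 states: "Follow up will continue until Day 45 for all subjects". SAP section 11.7.1 likewise defines completion by the Day 45 assessment. Protocol section 7.3.4 (Table 6) gives the sampling days for nasal strips and washes in inpatients as "Day 1, 3, 5, 8, 16, 24, 32; also at discharge or Day 45". For discharged subjects, a footnote to Table 4 in protocol section 7.1 reads: "Blood samples will be collected for exploratory biomarkers at PT Day 3, and at Study Day 45".

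**The concern.** The condition is an operative derivation rule that decides whether a value exists, and it is written in weeks in a study that runs for six and a half. A programmer who follows it produces no AUC(0-45) values at all. One who notices the problem must choose a replacement without guidance: drop the condition, read it as Day 24, or set some other day. With 10 subjects enrolled, that unwritten choice decides who appears in the plots and how much of each value is imputed. The SAP synopsis says that all final-analysis decisions are made before unblinding, so this one should be on paper by then.

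**Working it through.** **Inputs**

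- Threshold: week 24 (SAP 11.6.5.1).
- End of follow-up: Day 45 (protocol 4.2; SAP 11.7.1).
- Inpatient biomarker days: 1, 3, 5, 8, 16, 24 and 32, plus discharge or Day 45 (protocol 7.1 Table 3; 7.3.4 Table 6).
- Biomarker samples after discharge: PT Day 3 and Day 45 only (protocol 7.1 Table 4, footnotes on blood and nasal samples).
- Timing of PT Day 3: "For 5 days treatment, PT Day 3 will be the same as Day 8 and will be a clinic visit" (protocol 7.1 Table 4).
- Length of the AUC(0-45) window: 45 − 1 = 44 days.

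The plan gives no numerical result for AUC(0-45), so there is no figure to reproduce. The check applies the rule to the schedule.

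**Step 1: can the condition be met?** 24 × 7 = Day 168 (Day 169 if 24 full weeks are counted after Day 1). The last scheduled assessment is Day 45, or 45/7 = 6.4 weeks, and 168 − 45 = 123 days. No inpatient or outpatient assessment is scheduled beyond week 24.

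**Step 2: apply the rule to six sampling patterns**, with the threshold as written and with Day 24 for comparison.

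| Pattern (sample days) | Beyond week 24 | Beyond Day 24 |
|---|---|---|
| Complete inpatient (1, 3, 5, 8, 16, 24, 32, 45) | missing | calculable |
| SAP example, Day 24 missing (1, 3, 5, 8, 16, 32, 45) | missing | calculable |
| SAP example, Day 45 missing (1, 3, 5, 8, 16, 24, 32) | missing | calculable |
| Discharged, Day 45 done (1, 3, 5, 8, 45) | missing | calculable |
| Discharged, Day 45 missed (1, 3, 5, 8) | missing | missing |
| Inpatient, last sample Day 24 (1, 3, 5, 8, 16, 24) | missing | missing |

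As written, all six are missing, including a complete schedule and both of the SAP's own examples. With Day 24, both examples compute, and the two patterns that stay missing are those with no late sample.

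**Step 3: what the condition protects against.** The share of the window filled by carry-forward is (45 − last sample day)/44.

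- No condition; discharged after 5 days of treatment, Day 45 missed: (45 − 8)/44 = 37/44 = 84%.
- Day 24 threshold, earliest qualifying sample (a discharge sample on Day 25): (45 − 25)/44 = 20/44 = 45%.
- Day 24 threshold, last sample on Day 32: (45 − 32)/44 = 13/44 = 30%.

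The 84% uses the one PT Day 3 timing that the protocol states. It is not a maximum, since an earlier last sample would be carried further.

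**Step 4: which panels a corrected threshold would fill.** Serum and nasal strips are scheduled after Day 24 for all subjects (inpatient Day 32, discharge, or Day 45). Nasal wash is optional. Bronchoalveolar lavage (BAL) depends on routine care: "BAL samples (for biomarkers) are requested only if the procedure/sampling is being carried out for routine management of the patient". Its last scheduled column is Day 6. The nasal-wash panels (Figures 6.4 and 6.5) and BAL panels (Figures 6.8 and 6.9) may therefore stay sparse or empty after the correction.

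**The case against.** The strongest reply is that this is a one-word slip. The surrounding bullets work in days, list Day 24 and carry values to Day 45, so a careful programmer would see what was meant. That bears on how serious the error is, but does not remove it. The line decides whether a value exists, the documents never state the intended threshold, and the obvious shortcut of ignoring it changes the result (Step 3).

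It is also fair to say that Day 24 is only an inference. It is a strong one, because Day 24 is a scheduled sample day and makes both worked examples computable, but the sponsor has to confirm it.

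A reader might go further and infer that the AUC(0-PT Day 3) panels are distorted, because that AUC is not divided by window length and early discharge both ends dosing and counts as a clinical response. The documents do not support that as a finding. The SAP already says that the time to PT Day 3, and with it the biomarker value, varies, although it names only premature study discontinuation as the cause. Protocol 4.2 stops the infusion at early discharge but lets oseltamivir continue, and the documents do not state from which last dose PT Day 3 then counts. The direction of any effect is also unknown: stopping treatment for worsening could shorten the window too, and deaths before response are coded as 99 days.

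**Conclusion.** The rule is wrong as written. On a literal reading AUC(0-45) is missing for 100% of subjects, and one of the three AUC windows in each of eight figures (6.2 to 6.9) is empty. This rests only on date arithmetic and on follow-up ending at Day 45, which both documents state.

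That Day 24 was meant is likely but is an assumption. The 45% and 84% carry-forward shares follow from the sampling schedule; the 84% also assumes 5 days of treatment and a missed Day 45 sample.

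The consequence is minor. The figures are exploratory, SAP section 2.1 makes every analysis descriptive and lists all data, and the study stopped after 10 subjects. It would be wrong to infer any effect on the primary efficacy or safety analyses, and no artefact has been shown in the AUC(0-PT Day 3) panels.

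**What to change.** In SAP section 11.6.5.1, replace week 24 with the intended study day and record the choice before unblinding. If Day 24 is confirmed, any sample after Day 24 qualifies: a discharge sample on Days 25 to 31, the Day 32 sample or the Day 45 sample. The text should also say whether the condition uses actual study day, as the AUC itself does. The condition should not simply be deleted.

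Add a note that the optional nasal-wash panels and routine-care BAL panels may remain sparse or empty. A fuller footnote on the causes of a varying PT Day 3 window is an optional clarification.

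The cost is one corrected threshold and a short note, with no new data. Subjects with no sample after Day 24 would have no AUC(0-45), as the condition appears to intend.

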11.6.6. Health Outcomes

The FLU-PRO Total score is computed as a mean score across all 32 items comprising the instrument. Total scores can range from 0 (symptom free) to 4 (very severe symptoms).

Six domain scores are also computed, representing symptom severity in each of the following body areas: Nose, Throat, Eyes, Chest/Respiratory, Gastrointestinal, and Body/Systemic. Each domain score is calculated as the mean of all items comprising the domain. Each FLU-PRO domain score also ranges from 0 to 4. Algorithms and instructions for computing scores for the FLU-PRO Total and domain scores (including rules for handling missing data) are provided below:

Domain	Items	Scoring	Minimum Data Requirement
Nose	Runny or dripping nose Congested or stuffy nose Sneezing Sinus pressure	Arithmetic mean of 4 items within Nose domain	3 of 4 items must be present to calculate domain score
Throat	Scratchy or itchy throat Sore or painful throat Difficulty swallowing	Arithmetic mean of 3 items within Throat domain	2 of 3 items must be present to calculate domain score
Eyes	Teary or watery eyes Sore or painful eyes Eyes sensitive to light	Arithmetic mean of 3 items within Eyes domain	2 of 3 items must be present to calculate domain score
Chest/Respiratory	Trouble breathing Chest congestion Chest tightness Dry or hacking cough Wet or loose cough Coughing Coughed up mucus or phlegm	Arithmetic mean of 7 items within Chest/Respiratory domain	5 of 7 items must be present to calculate domain score
Gastrointestinal	Felt nauseous Stomach ache How many times did you vomit? How many times did you have diarrhea?	Arithmetic mean of 4 items within Gastrointestinal domain	3 of 4 items must be present to calculate domain score
Body/Systemic	Headache Head congestion Felt dizzy Lack of appetite Sleeping more than usual Body aches or pains Weak or tired Chills or shivering Felt cold Felt hot Sweating	Arithmetic mean of 11 items within Body/Systemic domain	8 of 11 items must be present to calculate domain score

Total	All above 32 items	Arithmetic mean of all 32 items within FLU-PRO	In the presence of missing data, the above conditions for the calculation of all domain scores must be met in order to calculate the FLU-PRO
			total score.

11.7. Appendix 7: Premature Withdrawals & Handling of Missing Data

11.7.1. Premature Withdrawals

Element	Reporting Detail
General	 Subject study completion (i.e. as specified in the protocol) was defined as a subject who completed the Day 45 assessment. Withdrawn subjects will not be replaced in the study. All available data from subjects who were withdrawn from the study will be listed and all available planned data will be included in summary tables and figures, unless otherwise specified.

